## **6.2.** Treatments Administered

Study Treatment Name:	Rituximab	Lilotomab	Betalutin
Dosage formulation:	As per approved product information	Single use vial containing 10 mL of lilotomab at a concentration of 5 mg/mL formulated in 40 mM phosphate buffer (35.5 mM disodium hydrogen phosphate dodecahydrate and 4.5 mM sodium dihydrogen phosphate dihydrate), pH 7.6, 8.7 mM NaCl, 5% sucrose and 0.02% polysorbate-20	Single use vial containing 8-10 mL of Lutetium (177Lu) lilotomab satetraxetan at a concentration of 0.78 mg/mL formulated in: 6.2 mM (0.48 mg/mL) Ammonium acetate, 161.5 mM (32 mg/mL) of sodium ascorbate, 0.81 mM (0.32 mg/mL) of diethylenetriamine pentaacetic acid (DTPA), 19.3 mM (0.77 mg/mL) of NaOH, 64 mg/mL of recombinant
			Albumin, 25.4 mM (3.5 mg/mL) of Sodium dihydrogen phosphate monohydrate and 77 mM (4.5 mg/mL) of NaCl.
			HCl is added in trace amounts to reach a pH in the Betalutin drug product of $6.9 \pm 0.5$ .
			Recombinant albumin constitutes for about 60% of the dry weight of the Betalutin drug product.
			The total radioactivity in the vial is in the range from 3222-3938 MBq.
Unit dose strength(s)/Dosage level(s):	375 mg/m 	40 mg	10 or 15 MBq/kg
Route of Administration	i.v. infusion through dedicated line or s.c. injection (as per site practice). s.c. injection (different dose) may only be used for the maintenance RTX dosing commencing at Week 14.	i.v. infusion through dedicated line	Slow bolus i.v. injection
Dosing instructions:	As per approved product information	Provided in drug specific Handling Plan	Provided in drug specific Handling Plan
Packaging and Labeling	As per approved product information	Treatment will be provided in a glass vial. Each vial will be labeled as required per country requirement.	Treatment will be provided in a glass vial. Each vial will be labeled as required per country requirement.

CONFIDENTIAL Study Number: LYMRIT-37-07 Version 4.0 04 Oct 2021

## 6.3. Preparation/Handling/Storage/Accountability

1. The Investigator or designee must confirm appropriate temperature conditions have been maintained during transit for all study drug received and any discrepancies are reported and resolved before use of the study drug.

- 2. Only patients enrolled in the study may receive study drug and only authorised site staff may supply or administer study drug. All study drugs must be stored in a secure, environmentally controlled, and monitored (manual or automated) area in accordance with the labeled storage conditions with access limited to the Investigator and authorised site staff.
- 3. The Investigator, institution, or the head of the medical institution (where applicable) is responsible for study drug accountability, reconciliation, and record maintenance (i.e., receipt, reconciliation, and final disposition records).
- 4. Detailed handling and preparation for the study drugs can be found in the appropriate Drug Handling Plans.
- 5. Further guidance and information for the final disposition of unused study drug are provided in in the appropriate Drug Handling Plans.

## 6.3.1. Preparation and administration of Betalutin

The total activity to be injected will be calculated volumetrically using the patient's body weight (kg) on the day of injection, the dose level, and decay correction factor (DC) to correct for physical decay of  $^{177}$ Lu. A table with correction factors is provided in the Drug Handling Plan. The dose will be capped for patients who weigh more than 130 kg (patients heavier than 130 kg will receive the dose for a 130-kg patient). Patients will receive Betalutin under supervision of a nuclear medicine specialist and the total radioactivity injected, the activity dose and the volume injected will also be recorded as above. The measured dose of Betalutin must be within  $\pm 10\%$  of the intended prescribed dose.

The total amount (volume to be drawn into the syringe) to be administered to a patient should be calculated as follows:

# Volume (ml) = $\frac{\text{dose } 10 \text{ or } 15 \text{ MBq/kg } x \text{ body weight (up to a max of } 130 \text{ kg)}}{\text{Decay corr factor } x \text{ radioactivity conc. (MBq/ml)}}$

Filling of the syringe should take place at a dedicated area for working with radioactive solutions. Site staff should wear medical gloves and eye protection during syringe filling to prevent contamination of the radioactive solution of skin and eyes. The individual responsible for Betalutin preparation will draw the correct volume of the study drug into a syringe, and control the correct activity for administration in a dose calibrator. Data regarding activity and volume to be injected for the various patients should be recorded on the study drug administration electronic case report form (eCRF) page.

The syringe should be shielded from radiation during preparation and administration of the patient doses. Aseptic technique should be used in the administration of Betalutin. Each patient will receive one dose in accordance with the treatment schedule. Betalutin will be given as a slow bolus i.v. injection using a shielded syringe driver. After administration, the syringe and

CONFIDENTIAL

line must be flushed with a minimum of 10 mL of sterile normal saline (0.9% NaCl), as detailed in the Drug Handling Plan. The equipment used in connection with the preparation and administration of the study drug, are to be treated as radioactive waste and should be disposed in accordance with hospital procedure for handling of radioactive material.

#### 6.3.2. Patient protection

The patient will receive verbal and written instructions in accordance with the hospital radiation safety policies and procedures regarding precautions, as necessary, after receiving the radioactive drug. Betalutin can be administered on an outpatient basis, dependent on local regulations.

#### 6.3.3. Administration of Rituximab

RTX will be ordered through the standard procedure at the study site. The study drug should be administered according to the approved product information (prescribing information) for RTX. Pre-medication consisting of an antipyretic and an antihistamine, e.g. paracetamol and dexchlorpheniramine or cetirizine, should always be administered before each infusion of RTX. The types of pre-medication used prior to RTX infusion will follow each study site routine, including any use of corticosteroids. The prepared RTX solution should be administered as an i.v. infusion through a dedicated line or s.c. injection (as per study site practice). Subcutaneous RTX may be used for the maintenance dosing only. RTX should not be administered as an i.v. push or bolus. The standard hospital procedure for infusion of RTX will be followed. If an AE occurs, the infusion will be stopped. When the symptoms have disappeared, the infusion will be re-started with 50% decreased infusion rate. Any AEs and information about pre-medication will be recorded in the eCRF. Other information such as drug accountability will be detailed in the RTX Drug Handling Plan.

#### 6.3.4. Administration of Lilotomab

Lilotomab will be delivered in vials of approximately 5 mg/mL lilotomab. Lilotomab for infusion will be prepared aseptically at the hospital and made ready for infusion as detailed in the Lilotomab Drug Handling Plan. Pre-medication consisting of an antipyretic and antihistamine medication should be administered before infusion of lilotomab.

The patient must be observed closely during the infusion and in the first hour after the infusion. Blood pressure and heart rate are measured before infusion and subsequently every 15 minutes until the patient seems clinically stable. The blood pressure and heart rate must be measured at 30 minutes and at 1 hour after the infusion has ended.

Temperature is measured before, and 1 hour after, the lilotomab infusion.

If the patient experiences any reactions, vital signs must be recorded frequently until the patient is stable. If any AEs occur, such as a drop in blood pressure, chills, fever and/or dyspnea, the infusion should be stopped. When the symptoms disappear, the infusion should be started again at 50% reduced infusion rate. The infusion rate of lilotomab may be adjusted depending on how well lilotomab is tolerated. Medication and supportive care measures should always be available during an infusion and information about pre-medication be recorded in the eCRF.

#### 6.3.5. Drug Accountability

The study drugs, i.e. RTX, Betalutin and lilotomab, should be kept in a secure place and must be administered only to patients in the study. For all three study drugs, an appointed individual is responsible for maintaining accurate records of the study drug. A list of study drug (received, administered to patients, destroyed) must be prepared and signed by the dedicated person responsible for drug handling.

When the drug accountability has been monitored by the Sponsor representative, the vials can be destroyed in accordance with hospital procedure. Betalutin should be stored for a minimum of 3 months (>10 half-lives) before disposal.

See the Drug Handling Plans for further details.

## **6.4.** Treatment Compliance

Site staff will check the administration volume for all RTX, lilotomab and Betalutin doses and record these in the patient's source documents and eCRF. Patients will receive Betalutin under supervision of a nuclear medicine specialist and the total radioactivity injected, the activity dose and the volume injected will also be recorded as described in Section 6.3.

## **6.5.** Supportive Care Guidelines

Persistent neutropenia (neutrophils/granulocytes <0.5 x 10^9/L) without fever

Patients with persistent neutropenia may be started on G-CSF 5  $\mu$ g/kg/daily given s.c. until the neutrophil count has reached the local hospital's reference range.

Neutropenia with fever (neutrophils/granulocytes <1 x 10^9/L; fever >38°C)

Blood cultures will be obtained from the patient. The patient should start on empiric antibiotics as long as clinically indicated. Provision of G-CSF to such patients is highly recommended.

Severe thrombocytopenia (platelets <20 x 10^9/L) or bleeding with platelets <50 x 10^9/L

Patients will be transfused with platelets to maintain a platelet count  $>20 \text{ x } 10^9\text{/L}$  or higher if clinically indicated to control bleeding. Epsilon aminocaproic acid may be given to patients with mucosal bleeding and platelet count  $<50 \text{ x } 10^9\text{/L}$ .

#### Severe anaemia (Haemoglobin <8.0 g/dL)

Patients will be transfused with packed red blood cells to maintain haemoglobin level >8.0 g/dL.

#### Hypersensitivity

In case of hypersensitivity reactions, study drug administration must be stopped immediately. Medicinal products for the treatment of hypersensitivity reactions, e.g. adrenaline, antihistamines and corticosteroids, must be available for immediate use in the event of an allergic reaction during administration of RTX, lilotomab or Betalutin.

#### Extravascular administration

If extravascular administration of Betalutin or lilotomab, i.e. leakage of the injection to the surrounding tissue is suspected, the administration must be terminated immediately. Rinse with isotonic saline, elevate the arm and gently massage the arm to facilitate lymphatic drainage.

## 6.6. Prior and Concomitant Therapy

Any medication or vaccine (including over-the-counter or prescription medicines, vitamins and/or herbal supplements) that the patient is receiving at the time of enrolment or receives during the study until 4 weeks following final RTX administration must be recorded in the eCRF along with:

- Reason for use
- The generic or trade name
- Start and end dates of administration
- Dosage information including dose and frequency

The Medical Monitor should be contacted if there are any questions regarding concomitant or prior therapy.

Haematology parameters should be carefully checked prior to administration of any other myelosuppressive therapy.

Warfarin should be changed to low-molecular heparin. The dose of low-molecular heparin should be temporarily reduced if platelets are  $<50 \times 10^9/L$ , and be temporarily stopped if platelets are  $<25 \times 10^9/L$ .

Prophylaxis with allopurinol for tumour lysis will be permitted at the discretion of the Investigator.

Use of live or attenuated vaccines is prohibited throughout the course of the study.

CONFIDENTIAL Study Number: LYMRIT-37-07 Version 4.0 04 Oct 2021

## 7. Discontinuation of Study Treatment and Patient Withdrawal / Discontinuation

## 7.1. Discontinuation of Study Treatment

The study may be discontinued at the discretion of the investigator or Sponsor in the event of the following:

- Occurrence of serious adverse reactions, including abnormalities in laboratory analysis and vital signs which by virtue of their nature, severity and duration are considered evidence that the safety of the study patients is no longer assured
- Medical or ethical reasons affecting the continued performance of the study
- Difficulties in the recruitment of patients
- Cancellation of drug development

## 7.2. Patient Withdrawal/Discontinuation from the Study

In accordance with the Declaration of Helsinki, each patient is free to withdraw from the study at any time. Investigator(s) also have the right to withdraw patients from the study in the event of illness, AEs, or other reasons concerning the health or well-being of the patient, or in the case of lack of cooperation.

Should a patient decide to withdraw after administration of the study drug(s) or should the Investigator(s) decide to withdraw the patient, all efforts will be made to complete and report the observations up to the time of withdrawal as thoroughly as possible. A complete final evaluation at the time of the patient's withdrawal (end of study visit) should be made within 28 days (± 3 days) of receiving the last study treatment administration if ending treatment per protocol, or within 7 days of taking the decision to withdraw if it occurs > 28 days after the last study treatment administration and an explanation given of why the patient is withdrawing or being withdrawn from the study. The reason and date for withdrawal must be noted in the eCRF. If the reason for withdrawal is a clinical AE or an abnormal laboratory test result, monitoring will continue until the outcome is evident. The specific event or test result(s) must be recorded in the eCRF. If the reason for withdrawal is due to disease progression, the study site should make all effort to continue with the safety monitoring.

Haematological toxicity was observed in the phase 1/2 LYMRIT-37-01 study, with nadir values 5 to 7 weeks after injection of Betalutin. It is advisable to monitor the haematology parameters of the withdrawn patients between 6 and 9 weeks after the last RTX administration or until recovery to CTCAE grade 1 or less.

Single patient study discontinuation is per definition, when the patient:

- has completed Month 24 administration of rituximab, per protocol or
- experiences one of the following situations before per protocol end of study:
  - withdraws consent to participate in the study
  - has died
  - is lost to follow up
  - has disease progression
  - starts further anticancer therapy or
- when the patient is withdrawn for a reason other than described above

CONFIDENTIAL

If the reason for withdrawal is death, the immediate cause of death should be noted, in addition to death caused by underlying disease, the investigator's judgement on possible relationship to study drug should be recorded in the eCRF.

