	Two cohorts of 3-6 patients will be initially evaluated for dose limiting toxicity before determining the subsequent Betalutin dose for the remainder of the study. Dose-escalation decisions will be made by the Investigator(s) and Sponsor following review of the safety data once haematologic recovery has occurred.
	After the last dose of rituximab, vital signs, ECG (final visit only), physical examination, haematology, serum biochemistry, Adverse Drug Reaction (ADR) and Adverse Events of Special Interest (AESI) will be collected at an end of study visit that will occur at least 28 days post last administration of study treatment. Patients in survival follow-up at time of Protocol v4.0 approval can have the EOS visit at their next scheduled visit or an earlier convenient time point.
Pharmacokinetics and biodistribution	Total radioactivity measurements in blood will be performed at certain intervals until Day 28. Mandatory at Radium Hospital (Oslo, Norway) only, otherwise optional. Patients will undergo SPECT imaging at certain time points in order to measure distribution of

	Betalutin in the body and calculate absorbed radiation dose to target organs/tissues and tumours.
Biomarker assessments	Biomarkers assessments including CD20 and CD37 expression in tumour tissue biopsy and immunophenotyping of circulating lymphocyte subsets (absolute cell counts), will be performed at various time points throughout the study
Other biomarker studies on additional samples	Biomarkers including but not exclusive to MRD (blood) and gene expression changes related to disease treatment in tumour tissue (archival or newly collected biopsy at screening, relapse or disease progression), will be assessed at various time points throughout the study. Patient's major histocompatibility complex (MHC) class I/II haplotype will be defined using peripheral blood (DNA) or saliva (DNA). Anti-tumour T-cell responses will be explored by flow cytometry after co-culture of peripheral mononuclear cells (blood) and autologous lymphoma cells (biopsy and/or needle aspirate), and other biomarkers at selected time points throughout the study at Radium Hospital (Oslo, Norway) only.
Statistical methods and data analysis	The safety analysis population will include all patients who received at least one dose of any study drug.

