### 4. Study Design

## 4.1. Overall Design

This protocol describes a Phase 1b open-label, single-arm, dose escalation study to investigate the activity and safety and preliminary efficacy of Betalutin combined with RTX in patients with FL who have received one or more prior therapies. It is planned that 6-12 evaluable patients will be enrolled in the study.

All patients will receive a single i.v. dose of RTX (375 mg/m^2) on Day -14, and then sequential i.v. administrations of lilotomab (40 mg) followed by Betalutin (10 or 15 MBq/kg) within 4 hours on Day 0. Patients will then be administered RTX (375 mg/m^2) i.v. on Days 7, 14, 21 and 28.

Patients will undergo clinical and laboratory assessments during screening/baseline and periodically during treatment as outlined in the Schedule of activities (Section 1.2). Two cohorts of 3-6 patients will be initially evaluated for DLT, in a 3+3 escalation pattern, before determining the subsequent Betalutin dose for the remainder of the study (Section 6.1).

Tumour-tissue biopsies and blood samples will be collected to study the mechanisms of tumour response to therapy as described in the biomarkers section (Section 9.4). The collection of these samples is optional and, at Radium Hospital (Oslo, Norway) only.

[figure not shown]
PET/CT and CT imaging (or MRI) will be performed at baseline and then at 3 and 6 months. CT with contrast (or MRI) will be performed at 12, 18, 24 months or until disease progression or withdrawal from the study for any other reason (whichever comes first).

Patients who achieve SD, CR or PR on their Month 3 imaging scan will be administered maintenance RTX 375 mg/m^2 i.v. or 1400 mg s.c. every 3 months for up to 2 years (8 infusions in total), or until disease progression or withdrawal from the study for any other reason (whichever comes first).

The schedule plan for dosing and imaging is illustrated in Figure 4-1.

Study Number: LYMRIT-37-07 Version 4.0 04 Oct 2021

Figure 4-1 Study dosing and imaging plan

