## 8.2.7. Visit 8, 9 and 10 (Week 5, 6 and 7) – Lab Visit

Procedures outlined in Table 8-10 will be performed at Visits 8, 9 and 10 (Weeks 5, 6 and 7).

Table 8-10 Procedures and assessments at Visit 8, 9 and 10 (Week 5, 6 and 7 [±2 days])

Assessment or Procedure	Explanation
Haematology	Including haemoglobin, platelet count, white blood cell count and differential (absolute count of neutrophils, lymphocytes, monocytes, eosinophils and basophils)
Serum biochemistry	Including sodium, potassium, calcium, magnesium, creatinine, urea, uric acid, ALP, ASAT, ALAT, LDH, GGT, glucose, total bilirubin and albumin

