## 8.2.11. Visits 16 (Month 3/Week 14) – Hospital Visit

Providing patient is deemed not to have PD following the Week 12 imaging scan (above), Rituximab maintenance dosing will commence, as outlined in Table 8-14.

Table 8-14 Procedures and assessments at Visit 16 (Week 14 [±7 days])

Assessment or Procedure	Explanation
Concomitant medication/therapy	Concomitant medication used since prior visit will be recorded
Physical examination	Any abnormal findings will be recorded in the AE record
Vital signs	Systolic/diastolic blood pressure, heart rate and body temperature
Rituximab administration	Weight, body surface area, dose administered, start and end time
$375 \text{ mg/m}^2 \text{ iv or } 1400 \text{ mg s.c.}$	of administration and pre-medication will be recorded
Adverse events	Any AEs occurring since prior visit will be recorded

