#### **8.2.19.** End of study visit – Hospital Visit

The end of study visit should occur:

- 28 days (± 3 days) post last rituximab administration for patients, who complete the study per protocol (Month 25/Week 108)
- Within 7 days of decision of withdrawing from the study is made if the decision occurs > 28 days post last administration of study treatment for patients who discontinue from the study before Month 24 (e.g. disease progression, start of new anti-cancer therapy, other reason) An end of study visit is not expected for patients, who discontinue due to death, lost to follow up or withdrawal of consent.

Safety follow-up procedures 4 weeks after administration of the final RTX study dose are outlined in Table 8-22.

Patients in survival follow-up at the time of Protocol v4.0 approval can have the EOS visit at their next scheduled visit or an earlier convenient time point

Table 8-22 Procedures and assessments at end of study visit

Assessment or Procedure	Explanation	
Concomitant medication	Recording of concomitant medication used since the previous visit	
Physical examination	Any abnormal findings will be recorded in the AE record	
Vital signs	Systolic/diastolic blood pressure, heart rate and body temperature	
ECOG	ECOG performance status	
Haematology	Including haemoglobin, platelet count, white blood cell count and differential (absolute count of neutrophils, lymphocytes, monocytes, eosinophils and basophils)	
Serum biochemistry	Including sodium, potassium, calcium, magnesium, creatinine, urea, uric acid, ALP, ASAT, ALAT, LDH, GGT, glucose, total bilirubin and albumin	
Adverse events	Any AEs / AESIs occurring since prior visit will be recorded	

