#### **9.2.4.** Reporting of adverse events

Any AEs that occur after a patient has signed the ICF and up to 12 weeks after their Betalutin or 4 weeks following their last maintenance RTX drug administration, must be reported, whether or not it is considered related to any of the study drugs. All AEs will be reported in the patient eCRFs. If more than one AE occurs, each event should be recorded separately. AEs and/or laboratory abnormalities shall be reported to the Sponsor according to the reporting requirements and within the time periods specified in the protocol. All AEs will be followed up until resolved or as clinically required. AEs that occur from 12 weeks after their Betalutin administration or 4 weeks after their last maintenance RTX drug administration, that are judged to be related to any of the study drugs will be reported when they come to the Investigator's attention.

Specific information about secondary malignancies such as leukaemia, MDS and aplastic anaemia or any other malignancy, will be collected up to 2 years after Betalutin administration or relapse of disease, including information about treatment given to the patient due to NHL (See Section 9.2.1.7).

Death is not defined as an AE but as an outcome of an AE. It is important that the event leading to the death be reported. It will be reported as an AE up to 12 weeks after their last study drug administration. Thereafter, death it will be collected in the eCRFs as survival information. It will be reported as the outcome of an ADR when it is judged as related to study drug.

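### Section 7.2 bases post-withdrawal blood counts on a nadir timed from Betalutin but times them from the last rituximab, so for early withdrawals the window opens 0 to 21 days after the nadir period ends

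*Combined protocol and SAP*

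**What the plan says.** Section 7.2 (Patient Withdrawal/Discontinuation from the Study) describes haematological toxicity in LYMRIT-37-01, "with nadir values 5 to 7 weeks after injection of Betalutin". The next sentence reads: "It is advisable to monitor the haematology parameters of the withdrawn patients between 6 and 9 weeks after the last RTX administration", with recovery to CTCAE grade 1 or less as the alternative end point.

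Betalutin is given on Day 0. Rituximab is given once on Day -14 and then, under Section 4.1, "i.v. on Days 7, 14, 21 and 28". Maintenance starts at Week 14 in patients without progression (Section 8.2.11: "Rituximab maintenance dosing will commence").

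For patients still on study, Section 8.2.7 provides haematology and biochemistry that "will be performed at Visits 8, 9 and 10 (Weeks 5, 6 and 7"). No section requires these counts after withdrawal.

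The other provisions for withdrawn patients are these:
- Section 7.2 continues monitoring after withdrawal for an adverse event or abnormal laboratory result, and asks for best efforts after progression. It sets no count times for either.
- The end of study visit includes haematology. The synopsis (Safety assessments) places these assessments "at an end of study visit that will occur at least 28 days post last administration of study treatment".
- Section 8.2.19 adds: "An end of study visit is not expected for patients, who discontinue due to death, lost to follow up or withdrawal of consent".
- Under Section 9.2.4, adverse events "up to 12 weeks after their Betalutin or 4 weeks following their last maintenance RTX drug administration, must be reported".

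**The concern.** The only reason Section 7.2 gives for the advised counts is the Betalutin nadir, yet the counts are timed from a different drug that is given up to four weeks later. A site following the sentence literally would begin the advised counts when the nadir period is ending or over.

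What is at stake is mainly patient safety. Symptomatic events would still be reported. The gap is low counts without symptoms, because the guidance in Section 6.5 on G-CSF for persistent neutropenia without fever and on transfusion for platelets below 20 x 10^9/L can be acted on only if a count is taken.

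**Working it through.** **Inputs.** Betalutin is on Day 0 (Section 6.1). The nadir period is 5 to 7 weeks after Betalutin (Section 7.2), so 5 x 7 = Day 35 to 7 x 7 = Day 49, which is 15 days counted inclusively. The advised window is 6 to 9 weeks after the last rituximab on day d, so d + 42 to d + 63.

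**Window against nadir period, nominal visit days.**

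| Last rituximab (d) | Window (d+42 to d+63) | Opening minus Day 49 | Nadir-period days inside window | d + 28 |
|---|---|---|---|---|
| Day -14 | Days 28-49 | -21 | 15 of 15 | Day 14 |
| Day 7 | Days 49-70 | 0 | 1 of 15 | Day 35 |
| Day 14 | Days 56-77 | 7 | 0 of 15 | Day 42 |
| Day 21 | Days 63-84 | 14 | 0 of 15 | Day 49 |
| Day 28 | Days 70-91 | 21 | 0 of 15 | Day 56 |

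**Visit tolerance.** Rituximab visits allow ±2 days. The window opening relative to Day 49 then ranges from -2 days (rituximab on Day 5, opening Day 47) to +23 days (rituximab on Day 30, opening Day 72). The best overlap for the Day 7 dose is Days 47-49, three days. For the later doses the earliest openings are Days 54, 61 and 68, so there is still no overlap.

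**Who lacks a nadir count.** The Week 5, 6 and 7 counts fall on Days 35, 42 and 49. A patient withdrawn before Day 35 has had none of them, on Days 35-41 one, on Days 42-48 two, and from Day 49 all three. Maintenance starts at Week 14, Day 98, which is 98 - 49 = 49 days after the nadir period ends, so withdrawals during maintenance are not affected.

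**End of study visit.** If it is held 28 days after the last rituximab (last column), it gives one count in the nadir period for a last dose on Day 7, 14 or 21, and none for Day 28. That timing is one reading only. Section 8.2.19 ties the 28-day rule to patients who complete per protocol, and its rule for earlier discontinuation covers decisions taken more than 28 days after the last dose. Timing for a decision within 28 days of the last dose is unclear. A single count also cannot show grade 4 lasting more than 7 days, the haematological dose-limiting toxicity criterion in Section 6.1.

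**Re-anchoring alone.** Counting the existing 6 to 9 weeks from Betalutin gives Days 42-63, which still misses Days 35-41. The added window has to start at Week 5.

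**Background rates (Section 2.2.2.1, 40 mg lilotomab and 15 MBq/kg).** Grade 4 neutropenia occurred in 7/36 = 19% (95% Clopper-Pearson interval 8-36%) and grade 4 thrombocytopenia in 6/36 = 17% (6-33%). Episodes lasting more than 7 days occurred in 2/36 = 5.6% for each (0.7-18.7%).

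**The case against.** The strongest reply is that the sentence concerns recovery, not the nadir. It ends with recovery to grade 1 or less. After a Day 28 dose its window is Days 70-91, Weeks 10 to 13, which sits near the scheduled late counts, and Section 2.4 says that cytopenias resolve by 3 months in most patients. This stands in part: that the advice aims at the nadir is inferred from the sentence before it, and the wording is advisory. It does not explain the rituximab anchor. Sections 2.3.3 and 4.2 expect rituximab to add little to neutropenia, thrombocytopenia or anaemia. Two patients with the same Betalutin day would have windows opening 70 - 49 = 21 days apart, according only to whether the last rituximab was on Day 7 or Day 28. The recovery clause sets an end, not a start.

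A second reply is that other provisions fill the gap. Section 7.2 also points to the Schedule of Activities, which contains the Week 5 to 7 counts, but it does not expressly require them after withdrawal. Monitoring linked to the reason for withdrawal has no stated times.

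A third reply also stands: the 5-to-7-week range says when the lowest values were seen. It is not how long each patient's counts stay low. The overlap figures describe the calendar, and a window opening on Day 49 to 70 could still find unresolved cytopenia.

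A reader might infer that withdrawn patients in general go uncounted through the nadir, or that the 19% and 17% are chances of a missed episode. The documents support neither. Patients withdrawn from Day 49 have already had the scheduled counts, and the percentages are chances that an episode occurs at 15 MBq/kg. They may be lower at 10 MBq/kg.

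**Conclusion.** The point holds: the advisory safety window is wrong as written because it is anchored to the wrong drug. Its importance is low to moderate. At nominal visit days it opens 0 to 21 days after the nadir period ends for every rituximab dose given on Days 7 to 28.

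The exposed group is narrow: patients withdrawn after the Day 7 rituximab and before the Week 5 to 7 counts are complete, for reasons other than an adverse event, a laboratory abnormality or progression, who still agree to attend. Those withdrawn before Day 35 have no nadir count unless an end of study visit happens to fall in Days 35-49. In a study of 6 to 12 patients this may be nobody. The documents give no withdrawal rate, so no study-level probability can be stated.

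A reader might also infer that the dose recommendation is compromised. The documents do not support that. Section 6.1 requires all doses and haematological recovery to grade 2 or better before a patient counts as evaluable, and Section 7.3 allows a further patient to be considered when too few are evaluable. The effect on the dose decision is small.

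The conclusion assumes that the advice is meant to serve the nadir named just before it, and that visits fall on or within 2 days of schedule.

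**What to change.** Add one sentence to Section 7.2:

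> Patients withdrawn after Betalutin and before completing the Week 7 count should be advised to have weekly haematology from Week 5 after Betalutin (or from withdrawal, if later) through at least Week 7, and then until recovery to CTCAE grade 1 or less.

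Keep the existing rituximab-timed advice for later withdrawals, including those during maintenance. The clinical team should set the exact schedule. An advisory sentence cannot oblige a patient who has withdrawn consent to attend.

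The cost is a few re-timed or extra blood counts: three on Days 35, 42 and 49 for a patient withdrawn before Week 5, then weekly only while counts have not recovered. The present window sets no frequency; sampled weekly at 6, 7, 8 and 9 weeks it would mean four counts.
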